7.4.2.2 Induction response

The patient response to induction treatment provides a measure of the patient-risk category. The commonly used definitions of good-risk (induction-responder) / poor-risk (induction non-responder) suggested below are adopted from Biondi et al. 2012. If this is not the definition that was used for a patient, information will be obtained with respect to the definition of risk.

- Good-Risk Group: Patients with both early response and complete remission at the end of induction e.g. Blast cell count < 1000/µl in peripheral blood after 7 days of Prednisone given in combination with chemotherapy drug(s) before induction is instituted or have M1/M2 BM at day 15 (after start of chemotherapy) or M1 BM at day 21 and achieve CR after induction period.
- Poor-Risk Group: Patients with poor early response to induction treatment or absence of complete remission at the end of induction e.g. Blast cell count ≥ 1000/µl in peripheral blood after 7 days of Prednisone given in combination with chemotherapy drug(s) before induction is instituted or have M3 BM at day 15 or M2/M3 BM at day 21 or do not achieve CR after induction period.
 - M1: <5% blasts, counting all nucleated cells, including erythropoiesis. In case of regenerating marrow with a high erythropoietic predominance, at least a total count of 100 non-erythropoietic cells should be counted.
 - M2: 5-25% blasts, counting all nucleated cells, including erythropoiesis. In case of regenerating marrow with a high erythropoietic predominance, at least a total count of 100 non-erythropoietic cells should be counted.
 - M3: >25% blasts in a BM aspirate.

7.4.2.3 Efficacy response

The efficacy of treatment with chemotherapy in combination imatinib (Glivec[®]) will be evaluated from diagnosis, and based on the tests performed (e.g. extramedullary, cerebrospinal fluid exam, hematological, MRD assessment data) by the treating physician and/ or designee for each patient to assess incidence of relapse and secondary malignancy.

7.4.2.4 Hematological response

Peripheral blood will be used to assess hematological response. Complete hematological remission requires that **all** of the following are present:

- Adequate bone marrow cellularity with a blast count < 5%
- No peripheral blood blasts
- ANC $\geq 1500/\mu l$
- Platelet count $\geq 100.000/\mu l$
- No evidence of extramedullary involvement

The loss of complete remission and thus the end of the duration of complete remission is defined as:

• \geq 5% blasts in bone marrow aspirate regardless of proportion of mature lymphocytes.

Progressive disease (relapse) is defined as the new appearance of any of the following:

- $\geq 25\%$ blasts in bone marrow aspirate
- Any increase of at least 25% in the absolute number of circulating leukemic cells.
- \geq 30% increase of Ph+ metaphase cells as assessed by standard cytogenetic analysis.
- Development (evidence) of extramedullary disease
- Other laboratory or clinical evidence of disease progression.

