7.3.1 Outcomes of interest

7.3.1.1 Event free survival

- Event free survival is defined as time from diagnosis to relapse at any site, development of a second malignant neoplasm or death (Section 7.4.2.3)
 - Relapse at any site defined as BM (e.g. via bone marrow assessment) or CNS (e.g. via cerebro-spinal fluid exam) or testis or other sites or any combination.
 - Second malignant neoplasm defined as presence of any secondary malignancy.

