7.3.1.5 Complete remission

- Complete remission is defined as < 5% blasts in bone marrow aspirate regardless of proportion of mature lymphocytes.
- The duration of complete remission is defined as the time from the date of first complete remission to the date of loss of complete remission (Section 7.4.2.4).

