7.7.4.3 Other secondary endpoints

The other secondary efficacy analyses will be the evaluation of the following outcomes:

- 1. Rate of Complete Remission (CR) CR is defined in Section 7.3.
- 2. Duration of first complete remission This is defined as the time between date of first complete remission to the date of loss of first complete remission.
- Rate of Complete Hematological Remission CHR response (Complete Hematological Remission) is defined in Section 7.3.
- 4. Rate of MRD response MRD response (Minimal residual Disease) is defined in Section 7.3.
- 5. Time to first transplantation This is defined as the time from date of diagnosis to the date of first transplantation.
- 6. Time to engraftment (neutrophil, platelet and both neutrophil/platelet) This is defined as the time from date of transplant to the date of engraftment.
- 7. Rate of engraftment failure
- 8. Rate of acute Graft versus Host disease
- 9. Rate of chronic Graft versus Host disease

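### Loss of complete remission and relapse follow unreconciled rules, so first remission can run past a patient's own extramedullary relapse, and 5 to <25% marrow blasts may or may not count for EFS

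*Protocol*

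**What the plan says.** - **Primary endpoint.** Protocol 7.3.1.1: "Event free survival is defined as time from diagnosis to relapse at any site, development of a second malignant neoplasm or death". It then lists the sites: "Relapse at any site defined as BM (e.g. via bone marrow assessment) or CNS (e.g. via cerebro-spinal fluid exam) or testis or other sites". No blast percentage is attached to marrow relapse there. For assessment it points to 7.4.2.3, which leaves relapse to the treating physician or designee on the basis of the tests performed.
- **Complete remission.** Protocol 7.3.1.5: "Complete remission is defined as < 5% blasts in bone marrow aspirate regardless of proportion of mature lymphocytes". Table 6-1 uses the same marrow-only definition.
- **Duration of remission.** Protocol 7.3.1.5 defines it as "the time from the date of first complete remission to the date of loss of complete remission" and refers to 7.4.2.4. Section 7.7.4.3 lists it among the other secondary endpoints: "This is defined as the time between date of first complete remission to the date of loss of first complete remission".
- **Loss of remission.** Protocol 7.4.2.4: "The loss of complete remission and thus the end of the duration of complete remission is defined as", followed by one item only, greater than or equal to "5% blasts in bone marrow aspirate regardless of proportion of mature lymphocytes".
- **Relapse.** Later in 7.4.2.4: "Progressive disease (relapse) is defined as the new appearance of any of the following". The items are marrow blasts of at least 25%, a rise of at least 25% in circulating leukemic cells, a rise of at least 30% in Ph+ metaphases, extramedullary disease, and an open item for other laboratory or clinical evidence of progression.

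**The concern.** A reader would expect the end of first remission and the relapse component of EFS to describe the same clinical event on the same date. Under these rules they need not. Two things are at stake. First, duration of first remission may keep accruing after the patient has relapsed outside the marrow, and would then include time after the relapse that EFS has already counted. Second, the same marrow finding can be an EFS event for one assessor and not for another, or can be dated later, because the protocol gives a numeric threshold in one place, none in another, and a discretionary item in a third. The second problem reaches the primary endpoint.

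**Working it through.** The main check is to apply the written rules to each type of finding in a patient already in first complete remission.

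| Finding | Relapse, hence EFS event? | Loss of complete remission? |
|---|---|---|
| Isolated CNS, testicular or other extramedullary relapse, marrow <5% | Yes (7.3.1.1; 7.4.2.4 extramedullary item) | No |
| Marrow blasts >=5% and <25%, no other sign | Undetermined: the 25% item is not met, but 7.3.1.1 has no threshold and the last item of 7.4.2.4 is open | Yes |
| Marrow blasts >=25% | Yes | Yes |
| Rise in circulating leukemic cells or Ph+ metaphases meeting the list, marrow <5% | Yes under 7.4.2.4 | No |

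The two rules are sure to agree only on marrow blasts of at least 25%.

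Row 1 follows directly from the text. Loss of remission has one criterion and it concerns marrow alone, so no reading of it lets an extramedullary relapse end remission. Durations should not be compared directly, because EFS starts at diagnosis and remission starts later. The comparison is of end dates: the EFS clock stops at the relapse, while the remission clock runs on to later marrow involvement or to the end of follow-up.

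Row 2 is an ambiguity, not a fixed error. Suppose marrow shows 10% blasts at one assessment and 30% at the next. Remission ends at the first assessment. EFS relapse is dated at the first if the physician uses the threshold-free marrow wording or the open item, and at the second if the numeric item is used.

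The protocol gives no event counts, so the size of row 1 can only be illustrated.

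- Input from the protocol: EFS 69.6% at 48 months in cohort 5 of COG-AALL0031 (5.3.1), and 50 patients as the planned minimum (7.5).
- Assumption 1, constant hazard: EFS at 60 months = 0.696^(60/48) = 0.696^1.25 = 0.636. Expected events = 50 x (1 - 0.636) = 18.2.
- Assumption 2, death without relapse at 0.02 per year and no other competing event: total hazard = -ln(0.696)/4 = 0.0906 per year, so the relapse share = (0.0906 - 0.02)/0.0906 = 0.78. Relapses = 18.2 x 0.78 = about 14.
- Assumption 3, 10% to 25% of relapses are isolated extramedullary: 14 x 0.10 = 1.4 and 14 x 0.25 = 3.5, that is 1 to 4 patients.

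No comparable figure can be given for row 2, because nothing in the protocol says how many marrow relapses are first seen between 5% and 25%.

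**The case against.** The best defence is that remission was meant to be a marrow endpoint. Loss at 5% blasts or more is the exact complement of remission below 5%, and extramedullary disease is covered elsewhere, in complete hematological remission and in EFS. That remission outlasts EFS in some patients is not in itself a mistake, since EFS also stops at a second malignancy. This stands as far as it goes: the remission definition agrees with its own loss rule. It does not explain why a patient with a recorded CNS or testicular relapse should be reported as still in first complete remission, and the protocol never says that this is intended.

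Three stronger readings are tempting, and the documents do not support them.

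- **That 5 to <25% blasts are never an EFS event, or that EFS is dated late for every such relapse.** Section 7.3.1.1 sets no marrow threshold, Sections 7.1.1 and 7.3.1.1 refer EFS to physician assessment under 7.4.2.3, and the relapse list closes with an open item. The finding may or may not be counted; it is not excluded.
- **That death in first remission is mishandled.** The protocol states no censoring rule for duration of remission, and its handling can properly be left to the analysis plan.
- **That patients from clinical trials and from routine care are judged by different relapse rules.** No section says so.

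It is also fair that the registry is descriptive, without formal testing (7.7), and that the clearest defect falls on one of the other secondary endpoints.

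**Conclusion.** The point holds in two parts of different strength. It is certain from the text that an extramedullary relapse with marrow blasts below 5% is an EFS event and does not end first remission, so duration of first remission is overstated for those patients. It is also certain that the protocol does not settle whether marrow blasts of at least 5% and below 25% are an EFS relapse; the direction and size of any effect on EFS are unknown.

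The figure of 1 to 4 patients in 50 is an illustration. It rests on a constant hazard extrapolated from one cohort, an assumed death rate without relapse, and an assumed extramedullary share. The contradiction does not depend on it. With about 18 events expected on the same basis, a few reclassified or redated events would be visible in the descriptive results. The definitions should be corrected, but this does not undermine the registry as a whole.

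**What to change.** Reconcile Protocol 7.3.1.1, 7.3.1.5, 7.4.2.4 and 7.7.4.3 as follows.

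1. Duration of first complete remission ends at the first relapse at any site, as counted for EFS, and on the same date.
2. One stated marrow threshold serves both loss of remission and marrow relapse. The sponsor chooses which; this review does not say which is right.
3. Section 7.3.1.1 states whether the relapse list in 7.4.2.4 governs EFS. If it does, the open last item needs enough definition to be applied alike across sites.

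If a marrow-only remission endpoint is in fact intended, label it as such and say that extramedullary relapse does not end it.

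The cost is wording in four sections. Marrow assessment and extramedullary involvement with CSF examination are already database items in Table 7-1, so no new assessments are needed.

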7.4.2.5 Molecular response

MRD assessments to detect BCR-ABL transcript will be evaluated at specific time-points (if available) to provide a measure of the molecular response. Biondi et al. 2012 define the 5 time-points as the following: post-frontline induction; pre-consolidation block 1, pre-consolidation block 2, pre-consolidation block 3, post-consolidation.

MRD assessments may be performed for example via quantitative real-time PCR of mononuclear bone marrow and peripheral blood cells or detection by flow cytometry. Data should be provided if available at the aforementioned time-points.

7.4.2.6 Transplant and engraftment

- Transplant (i.e. date of transplantation, phase of transplantation, type of transplantation, source of transplantation, relationship to donor).
- Time to engraftment, engraftment failure (i.e. date, neutrophil/platelet engraftment success yes/ no, engraftment failure yes/no).
- Presence of graft versus host disease (i.e. chronic graft versus host disease presence yes/ no, acute graft versus host disease presence yes/no).

7.4.2.7 Physical examination

A general physical examination would include the examination of general appearance, and vital signs (e.g. blood pressure [BP] and pulse), although the extent of the examination is at the discretion of the treating physician and/ or designee.

Significant findings that were present prior to first dose of imatinib must be included in the Relevant Medical History page on the patient's eCRF. Significant new findings that begin or worsen after start of treatment with imatinib (Glivec[®]) must be recorded on the Adverse Event page of the patient's eCRF.

7.4.2.8 Performance status

Performance status may be measured using the Lansky/ Karnofsky Performance Status Score. Wherever possible, the same performance scale used at baseline assessment should be maintained for the duration of follow-up.

7.4.2.9 Height and weight

Height in centimeters (cm) and body weight (to the nearest 0.1 kilogram [kg] in indoor clothing, but without shoes) will be captured in the database, if available.

7.4.2.10 Tanner stage and development assessments

Tanner staging will be evaluated as a measure of pubertal status (Tanner 1-5). Data corresponding to the age of menarche for girls and the age of adrenarche for boys will be captured, if available.

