6 Research question and objectives

The main objective is to collect data to describe long-term clinical outcomes measured by event-free survival (EFS), overall survival (OS) and long-term safety in newly diagnosed Ph+ ALL pediatric patients treated with imatinib in combination with chemotherapy

This multi-center, registry is not designed to test a formal hypothesis, but has been initiated as part of the post-marketing commitment to the type II variation EMEA/H/C/000406/II/80, in order to address the limitations related to the limited size of the efficacy and safety database (up to 92 patients evaluated for efficacy and 220 patients evaluated for safety in prospective studies).

Objectives and related main variables under study are described in Table 6-1 below.

Confidential

Table 6-1 Objectives and related main variables

Objective	Main Variables	Analysis
Primary		Refer to Section 7.7
To evaluate long term clinical outcome measured by event-free survival (EFS, events defined as: relapse, death , secondary malignancies)	EFS, defined as time from diagnosis to relapse at any site, development of a second malignant neoplasm or death.	
Main secondary		
To evaluate overall survival	OS, defined as time from diagnosis to death from any cause.	
To evaluate safety	Adverse events and serious adverse events in the observation period.	
Other secondary		
To evaluate hematological remission status	Hematological remission status. Complete hematological remission requires that all of the following are present: a) Adequate bone marrow cellularity with a blast count < 5%, b) No peripheral blood blasts, c) ANC ≥1500/µl, d) Platelet count ≥100.000/µl, e) No evidence of extramedullary involvement	
To evaluate minimal residual disease (MRD) response	MRD response evaluated via detection of BCR-ABL transcript (e.g. determined via quantitative real-time PCR of mononuclear bone marrow and peripheral blood cells or detection by flow cytometry).	
To evaluate duration of complete remission	Complete remission and duration of complete remission (CR, defined as <5% blasts in bone marrow aspirate regardless of proportion of mature lymphocytes).	
To evaluate time to transplantation, time to engraftment, engraftment failure, graft versus host disease	Transplant and time to transplant from diagnosis. Time to engraftment and engraftment failure Incidence of graft versus host disease (acute and chronic)	

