To assess growth and development	Standard measures of growth and development e.g. general physical examination, height, weight, and Tanner staging.	

7 **Research methods**

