7.3.1.7 Assessment of growth and development

• Physical examination information, including the standard growth & development measures of height and weight, and sexual maturity (Section 7.4.2.7, Section 7.4.2.9 and Section 7.4.2.10).

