7.7.5.1 Growth and development

Growth and development data collected during the study will be summarized descriptively at each relevant time point. These data consist of height, height velocity (difference of height over 1 year), weight, weight velocity (difference of weight over 1 year) reported as standard deviation score (SDS, also called z-score), the age at the larche (Tanner stage 2 for breast development) and menarche for girls, the age of adrenarche for boys as well as the Tanner stage assessment.

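### The only dated pubertal milestone for boys is age at adrenarche, an adrenal event, so the boys' onset-age summary does not date gonadal puberty

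*Protocol*

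**What the plan says.** The growth and development objective is listed among the other secondary objectives in Table 6-1 (section 6). Its variables are given as "Standard measures of growth and development e.g. general physical examination, height, weight, and Tanner staging". Section 7.3.1.7 describes the outcome as physical examination information, "including the standard growth & development measures of height and weight, and sexual maturity".

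Section 7.4.2.10 then names two kinds of pubertal data:

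- Stage: "Tanner staging will be evaluated as a measure of pubertal status (Tanner 1-5"), with no restriction by sex.
- Ages: "Data corresponding to the age of menarche for girls and the age of adrenarche for boys will be captured, if available".

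Table 7-1 schedules Tanner staging for entry in the clinical database at baseline, on-treatment follow-up, end of treatment, post-treatment follow-up and study evaluation completion.

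Section 7.7.5.1 lists what is summarised. For girls it is the age at thelarche ("Tanner stage 2 for breast development) and menarche for girls"). For boys it is "the age of adrenarche for boys as well as the Tanner stage assessment". The summary is descriptive, by time point, on the safety set.

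**The concern.** The stated targets are pubertal status and sexual maturity. Thelarche and menarche both depend on ovarian function, so a dated summary of them follows gonadal puberty in girls. Adrenarche is the maturation of adrenal androgen secretion and does not depend on the testis. A boy with testicular failure or central delay can have an ordinary age at adrenarche.

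The variable chosen for boys therefore misses the event that the outcome is meant to date. At stake is the long-term safety description: a reader of the final report who sees an unremarkable onset age in boys could take it as reassurance about gonadal development, which it is not. The two sexes' age summaries would also sit side by side while describing different biological events.

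**Working it through.** The protocol attaches no figure to this point, so there is nothing to reproduce. The check sets the relevant sections against each other.

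**1. Dated milestones by sex**

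| | Captured (7.4.2.10) | Summarised (7.7.5.1) | Organ on which it depends |
|---|---|---|---|
| Girls | menarche | thelarche (breast stage 2), menarche | ovary |
| Boys | adrenarche | adrenarche | adrenal gland |

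Neither section names an age at genital stage 2 or at any other testicular event. The same choice stands in the assessment section and the analysis section, so it is a fixed definition and not a detail left open.

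**2. What the boys' age variable can register.** Suppose gonadal onset is delayed by d years and adrenal maturation is unchanged. The shift in age at adrenarche is then 0 for any d, while a girl's thelarche age would shift by d. This follows from the definition of the variable. It is not an estimate of what will happen in this cohort.

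**3. What Tanner staging adds.** It is in the database at five scheduled points (Table 7-1) and is summarised in section 7.7.5.1. A boy who stays at an early genital stage would be visible there. Two gaps remain:

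- The protocol does not say which component is staged in boys. A pubic-hair stage is open to the same adrenal influence as adrenarche.
- A tabulation of stage by time point gives no age at onset, whereas girls get one.

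**4. Who can contribute an onset age.** Section 7.2.2 admits patients from 1 to under 18 years at diagnosis. Section 5.2 gives a median age of 9 to 10 years for pediatric Ph+ ALL. Section 7.1.4 requires at least 5 years of follow-up from the start of imatinib, unless the patient discontinues early. Treating diagnosis and start of imatinib as close together:

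- youngest: 1 + 5 = about 6 years at minimum follow-up;
- median: 9 + 5 = 14 to 10 + 5 = 15 years;
- oldest: just under 18 + 5 = just under 23 years.

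A patient near the median is thus followed into the mid-teens, so the question is relevant to this cohort. The youngest may still be prepubertal at the end, and the oldest may be pubertal already at diagnosis. The protocol gives neither the sex ratio nor the age distribution, so the number of boys with an onset under observation cannot be calculated.

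**5. Related mismatch.** Section 7.7.5.1 summarises age at thelarche, but section 7.4.2.10 does not list it among the ages captured. It would have to be derived from serial breast staging, which is the same kind of derivation that boys lack.

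**The case against.** The strongest reply is that Tanner staging, not adrenarche, is the protocol's stated measure of pubertal status. It comes first in section 7.4.2.10, is named in Table 6-1, is scheduled throughout and is summarised for everyone. This stands. A reader might infer that puberty in boys is measured by adrenarche alone and that delayed or absent gonadal puberty could never show. The documents do not support that: staging could show it, provided the genital component is recorded.

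A second reply is that a derivation of onset age from stage data belongs in the analysis plan, and that the eCRF may already separate the components. Neither document is at hand, and silence on the component is not in itself an error. But the protocol is not silent on the age variable. It names adrenarche for boys in two sections, and an analysis plan that followed it would summarise that variable.

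A third reply is that the consequence is modest. The objective is secondary, all analyses are descriptive, no comparison of boys with girls is planned, and the ages are captured only where charts hold them. This also stands, and it limits the weight of the point. A reader might also take every boy in the registry to be affected. Boys already pubertal at entry, or still prepubertal at the end, have no onset under observation, so that reading is too broad.

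**Conclusion.** The point holds in a limited form. The dated milestone for boys is an adrenal event, it has no gonadal counterpart to thelarche and menarche, and the boys' onset-age summary therefore does not date gonadal puberty. Tanner staging partly compensates, but its component in boys is unspecified and it gives no age.

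The effect is confined to one descriptive variable of a secondary objective. Event-free survival, overall survival and the adverse event summaries are not touched. The conclusion rests on the definition of adrenarche and on the wording of sections 7.4.2.10 and 7.7.5.1. It needs no assumption about sex ratio or about the size of any delay. The change is worth making because it is cheap and the registry exists to describe long-term outcomes.

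**What to change.** In sections 7.4.2.10 and 7.7.5.1:

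- Name age at Tanner genital stage 2 as the boys' onset milestone, parallel to breast stage 2 in girls, derived where available from the staging already scheduled in Table 7-1.
- List age at breast stage 2 in section 7.4.2.10 as well, so that the captured and summarised ages agree.
- State that genital stage (boys) or breast stage (girls) is recorded separately from pubic-hair stage.
- Keep adrenarche or pubic-hair onset only as a separate descriptive item.
- Report, beside the onset ages, how many patients were already at stage 2 or above at baseline and how many were still at stage 1 at last assessment. A boy with absent puberty has no onset age and would otherwise drop out of the summary.

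The cost is wording, a derivation rule and possibly an eCRF field. No visit or procedure is added, so the registry stays non-interventional. Section 7.1.1 allows retrospective additions while the database is open, so stages already in charts could still be entered.

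The drawback is precision. Onset is known only to lie between the last record at stage 1 and the first at stage 2 or above, and only for boys who enter puberty under observation. If staging were recorded only as often as the minimum yearly data update (12 ± 2 months), that interval would be 12 − 2 = 10 to 12 + 2 = 14 months. Staging follows local practice, so actual intervals may be shorter or longer.
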